### 1.7 Validation of clinical tests

In order for submaximal heart rate recovery to be used as a peri-operative risk measure, we need to demonstrate scientific validity. There are several types of validity which can be applied to a clinical test. Face validity is where the theoretical basis behind the measurement is scientifically sound and so taken at “face-value” represents what it purports to measure. Criterion validity is where the test is compared to a “gold-standard” criterion. Concurrent validity is where both measurements are taken concurrently and the test has the ability to distinguish between different groups of patients, for example, between patients at high or low risk of complications. Predictive validity is observed when the measurement identifies patients who develop a specific outcome. Construct validity is comparison of the measure against “constructs” used in place of the gold-standard. Table 1 details the types of validity and their application in the validation of submaximal heart rate recovery as a peri-operative risk stratification tool.

Table 1. Types of validity and how these will be applied to HRR measurement. Modified from Ferguson et al.

Validity Measure	Explanation	Example as applied to HRR
Criterion validity	Test corresponds to a gold standard measure	HRR is associated with cardiopulmonary exercise testing derived indices – anaerobic threshold (AT) and peak $VO_2$ ( $VO_{2\text{peak}}$ )
Concurrent validity	Test is able to distinguish between groups that theoretically it should be able to distinguish between	High risk patients as determined by CPET  : 
 
• AT <10ml/kg/min
 
• <math>VO_{2\text{peak}} < 20\text{ml/kg/min}</math>
 
• <math>VE/VCO_2</math> at AT >34
 

Predictive validity	Test is able to predict something it theoretically should be able to predict	Identifies patients with poor post-operative outcomes e.g. myocardial injury
Construct validity	Extent to which the test corresponds to other measurements that theoretically support the concept (or construct) being measured	Association observed between HRR and clinically used pre-operative risk predictors e.g. METs score, DASI, Clinical frailty score, Revised cardiac risk index, P-POSSUM and NT-ProBNP

### 1.8 Rationale

Effective pre-operative functional capacity testing is part of the evolving peri-operative care pathway which aims to involve patients and their families in integrated and shared decision making to improve patient experience and outcome, and also cost-effectiveness of the surgical pathway within the NHS. Heart rate recovery after submaximal exercise testing offers a widely available and economical additional way to identify high risk patients in order to discuss risk with patients and to allocate resources correctly e.g. elective post-operative critical care. This is the first study seeking to validate submaximal HRR in an intermediate/high risk surgical population.

### **1.9 Aim and Hypotheses**

- To assess predictive, criterion and construct validity of submaximal heart rate recovery as a peri-operative risk measure in patients undergoing intermediate/high risk surgery
- Heart rate recovery following submaximal exercise is a valid predictor of post-operative myocardial injury in patients undergoing intermediate/high risk surgery and when compared to current peri-operative risk measures, HRR fulfils both criterion and construct validity.

## **2. Study Plan**

### **2.1 Study Design**

Multi-centre prospective observational cohort study of 95 patients presenting for intermediate/high risk elective surgery.

### **2.2 Study Setting**

Multi-centre study led by the Golden Jubilee National Hospital (GJNH). The other collaborating centres are the Queen Elizabeth University Hospital (QEUH), University Hospital Hairmyres (UHH) and University Hospital Crosshouse (UHC). The centres comprise a mixture of tertiary referral centres and district general hospitals in the West of Scotland.

### **2.3 Study Summary**

Intermediate/high risk surgical patients will be identified at surgical multi-disciplinary meetings, clinics or at anaesthetic pre-assessment clinic. All patients will have baseline demographics, subjective functional capacity and risk scores recorded pre-operatively (Table 1). NT-proBNP and troponin samples will be taken. A cohort of patients at UHH and UHC will undergo CPET testing as per their routine pre-operative care. A sub-study of the CPET patients will compare submaximal heart rate recovery with maximal heart rate recovery, and also patients' perceptions of the two different tests.

Submaximal HRR will be measured and recorded at pre-assessment clinic or on admission to hospital if prior to the day of surgery. Patients will undergo their operation as standard with clinicians blinded to the HRR result.

The primary outcome is myocardial injury as defined by a troponin level above the 99th centile upper reference limit and a 20% change (increase or decrease), therefore troponin levels will be measured at baseline and on post-operative days 1 and 2. Secondary outcomes will include quality of life questionnaires, clinical indicator outcomes and post-operative complications measured up to 1 year post-operatively (Table 2).

*Table 2 Indication of timeline for both pre-operative measures and post-operative measures. METS = metabolic equivalents; DASI = Duke Activity Status Index; CFS = Clinical Frailty Score; RCRI = Revised Cardiac Risk Index; SORT = Surgical Outcome Risk Tool; POSSUM = Physiological and Operative Severity Score for the enumeration of Mortality and Morbidity; QoR = quality of recovery score; DaOH = days alive and out of hospital; AKI = acute kidney injury; MAKE = major adverse kidney events; CVS = cardiovascular complications; MACE = major adverse cardiac events; PPC = post-operative pulmonary complications*

Test	Preop	D1	D2	D7	D14	D30	M3	1 year
NT-proBNP	X							
Troponin	X	X	X					
METs	X							
DASI	X							
CFS	X							
RCRI	X							
SORT	X							
P/V-POSSUM	X							
QoR-15	X		X					
EQ-5D-5L	X						X	X
DaOH						X		
4AT				X				
AKI				X				
MAKE					X			
Infective			X					
CVS			X					
MACE					X	X		X
PPC			X					
Mortality					X	X	X	
Admission to ICU				X				
Readmission to hospital					X			
LOS (+/- inhosp mortality)						X		

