### **3. Objectives and outcomes measures**

#### **3.1 Primary outcome measures**

Post-operative myocardial injury as defined by the 4th Universal definition of Myocardial Infarction, with troponins measured pre-operatively and on days one and two post-operatively.

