#### **3.1.1 Rationale for primary outcome**

Post-operative myocardial injury is a well-recognised and widely used outcome measure of the cardiovascular effects of surgery and anaesthesia. It is independently associated with an increased risk of post-operative death in the absence of myocardial infarction. Troponin assays are a relatively cost-effective test to add to the peri-operative blood tests the majority of patients will undergo as part of their routine care. Recent studies have demonstrated that approximately 90% of troponin elevation occurs within the first two days post-operatively.

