### 4.2 Exclusion criteria

1. Pregnancy
2. On-going participation in any investigational research which could undermine the scientific basis of the study
3. Presence of any of the American Thoracic Society's contraindications to exercise testing (Appendix 1)
4. Previous intermediate/high risk surgery within three months prior to recruitment
5. Previous participation in the VERVE study at any time
6. Presence of cardiac pacemaker or implantable cardioverter-defibrillator.

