### 4.2.1 Rationale for inclusion/exclusion criteria

Aging is a cardiovascular risk factor. Previous studies have identified patients over 65 years or age over 40-45 years with one peri-operative risk factor as at increased risk of post-operative cardiovascular events. Proportionally, the majority of patients undergoing high risk surgery are aged over 59 years so including patients over 50 years of age should allow for a

cohort at increased risk of peri-operative myocardial injury whilst ensuring a degree of generalisability within non-cardiac surgery patients.

Although incorporating orthostatic heart rate recovery into the protocol, our main intervention relies on patient's being able to step well enough to generate a heart rate response of approximately 60% predicted maximum heart rate (HRmax). This criterion will also therefore exclude a proportion of patients whose mobility may be limited by musculoskeletal problems rather than impaired cardiovascular fitness. The presence of a cardiac pacemaker may alter the heart response to exercise and recovery; an implantable cardioverter-defibrillator (ICD) may be stimulated if the patient heart rate exceeds that which is expected.

The prevalence of post-operative myocardial injury after low risk surgery is low, and so may be a difficult signal to identify. Low risk surgery is often performed as day-case and so post-operative monitoring is difficult in this cohort. In order to facilitate generalisability of the measure, patients undergoing intermediate/high risk surgery as defined by the ESC/ESA i.e. >1% risk of cardiovascular death or myocardial infarction will be recruited. Identifying patients by surgical risk rather than individual patient risk should allow a wide variety and degree of co-morbidity.

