## 5. **Study Conduct**

### 5.1 **Recruitment**

Each recruiting hospital and surgical specialty has its own referral pathway from surgical outpatient clinic and diagnosis through to pre-assessment and admission for surgery. Therefore each pathway will vary, but in general we will aim to identify patients as early as possible in their pathway either via surgical referral or pre-assessment clinic. Eligible patients will ideally speak with a member of the research team face to face and take the Participant Information Sheet home to consider and discuss with others. Due to the rapid turnaround of surgical referrals to surgery however, some patients may receive a cover letter and Patient Information sheet in the post with the paperwork about their procedure. This will allow for telephone discussion prior to consent. We will aim to consent and collect all pre-operative data, including performing the submaximal exercise test at pre-assessment clinic or on the ward if the patient is admitted prior to the day of surgery. Exercise testing will not be performed on the day of surgery.

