# **7. Statistical Considerations**

Our group has developed novel indices for measuring heart rate recovery including area under the curve and non-linear mixed effects modelling. This study is part of a higher degree programme (MD by research; [name]) which will encompass statistical methodology as an iterative process. The primary method of measuring HRR will be effort-corrected area under the curve (EC-AUC) but our other methods will also be examined. A formal statistical analysis plan will be written and agreed between the principal investigator (CH) and chief investigator (BS) prior to any data analysis.

All statistical analysis will be carried out using R-studio.

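### As written, the primary-endpoint rule lets a troponin that only falls from a raised pre-operative value be scored as post-operative myocardial injury

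*Combined protocol and SAP*

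**What the plan says.** Section 2.3 gives the only working rule for the primary outcome that is visible in the document: a troponin above the 99th "centile upper reference limit and a 20% change (increase or decrease"). The same sentence draws the sampling schedule from that rule: "therefore troponin levels will be measured at baseline and on post-operative days 1 and 2". The pre-operative sample is therefore part of the series to which the rule applies.

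Section 3.1, the formal endpoint section, calls the outcome post-operative myocardial injury and refers to the Fourth Universal Definition, "with troponins measured pre-operatively and on days one and two post-operatively". It adds no direction, no reference sample and no rule for a raised baseline.

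Section 3.1.1 justifies the endpoint as a measure of the cardiovascular effects of surgery and anaesthesia, and notes that "approximately 90% of troponin elevation occurs within the first two days post-operatively".

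Three other places bear on who can have a raised baseline:

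- Section 4.2 excludes on "Presence of any of the American Thoracic Society" contraindications in Appendix 1, but not on a raised troponin.
- Section 4.2.1 says: "Identifying patients by surgical risk rather than individual patient risk should allow a wide variety and degree of co-morbidity".
- Section 5.1 aims to "collect all pre-operative data, including performing the submaximal exercise test at pre-assessment clinic" or on the ward before the day of surgery, with no stated maximum interval to the operation.

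On analysis, Section 7 says: "A formal statistical analysis plan will be written and agreed" before any data analysis.

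**The concern.** The endpoint is meant to capture injury caused by the operation. A patient whose troponin is already raised at pre-assessment and then declines has shown no post-operative rise, yet can meet the rule in Section 2.3. That does not fit the label in Section 3.1 or the rationale in Section 3.1.1. It also weakens the predictive-validity aim in Section 1.9, because the elevation was there before surgery.

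The primary analysis (Section 7.2) is the AUROC of heart rate recovery for this binary label, and only about 22 events are planned. One or two wrong labels would show in the estimate. The direction of the error cannot be known in advance. Fall-only patients unrelated to heart rate recovery pull the AUROC toward 0.5, while fall-only patients who have existing cardiac disease and poor recovery push it up. Two assessors could also score the same series differently and both cite the protocol.

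**Working it through.** **1. Scoring example series against the written rule.** Values are multiples of the 99th-centile limit, in the order pre-operative, day 1, day 2. The series are made up to test the wording.

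- 2.0, 1.5, 1.4: every value is above the limit. 1.5/2.0 − 1 = −25% and 1.4/2.0 − 1 = −30%. The rule is met, although troponin only fell.
- 1.3, 0.9, 0.8: only the pre-operative value is above the limit. 0.9/1.3 − 1 = −31% and 0.8/1.3 − 1 = −38%. The rule is met unless the raised value must be post-operative, which Section 2.3 does not say.
- 1.5, 1.7, 1.3: 1.7/1.5 − 1 = +13%, then 1.3/1.7 − 1 = −24%. This is met if day 1 to day 2 counts as the pair. It is not met against the pre-operative sample, where 1.3/1.5 − 1 = −13%. The text does not say which pair applies.

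**2. Reproducing the plan's sample size (Section 7.1).** Inputs: AUROC 0.5 against 0.7, incidence 24.5%, type 1 error 0.05 (taken as two-sided, which reproduces the plan's figure), power 80%, dropout 5%. The Hanley–McNeil variance for n₁ events and n₀ non-events is

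Var(A) = [A(1−A) + (n₁−1)(Q₁−A²) + (n₀−1)(Q₂−A²)]/(n₁n₀), with Q₁ = A/(2−A) and Q₂ = 2A²/(1+A).

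Power = Φ{[(A−0.5) − 1.96·SE(0.5)]/SE(A)}.

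Expected events are 0.245 × 90 = 22. With 22 events and 68 non-events, SE(0.5) = 0.0712 and SE(0.70) = 0.0685. Then (0.20 − 1.96 × 0.0712)/0.0685 = 0.88, which gives power of 81.1%. Dropout: 90/0.95 = 94.7, rounded up to 95. The plan's 90 and 95 both reproduce.

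**3. Effect of k fall-only events unrelated to heart rate recovery.** k is an assumption. These events are given an AUROC of 0.50 against non-events, and the total stays at 90.

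- Replaced: 22 labelled events, k of them false. A = (1−k/22)·0.70 + (k/22)·0.50.
- Added: 22+k labelled events and 68−k non-events. A = (22·0.70 + k·0.50)/(22+k).

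| k | Case | AUROC | Power under the written rule | Power once they are removed |
|---|---|---|---|---|
| 1 | Replaced | 0.691 | 77.2% | 79.8% (21/69) |
| 1 | Added | 0.691 | 78.6% | 81.1% (22/68) |
| 2 | Replaced | 0.682 | 72.9% | 78.3% (20/70) |
| 2 | Added | 0.683 | 76.2% | 81.1% (22/68) |

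**4. Opposite direction.** If two replaced events instead had an assumed AUROC of 0.80 to 0.90 against non-events, the estimate would read (20/22)·0.70 + (2/22)·0.80 = 0.709, up to (20/22)·0.70 + (2/22)·0.90 = 0.718.

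**5. Random variation alone.** A simulation of 1,000,000 patients took three log-normal samples around a stable 1.5 times the limit. The within-patient coefficient of variation (CV) is assumed to be 5% or 10%; the documents give none. With the pre-operative sample as comparator, the two-directional rule labels 1.1% or 26.3% of such patients. A rise-only rule labels about 1% or 16.4%. The difference, 0.15% or 9.9%, is patients labelled only through a fall of at least 20%. Some of these also had a post-operative rise of under 20%. True falls from a raised baseline would come on top and cannot be estimated from the documents.

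**The case against.** The strongest reply is that Section 3.1, not the Study Summary, is the formal definition. It says post-operative and adopts a published definition by reference, and other sections use the same word. The cited source is not available here and may settle timing and comparator. This stands as a limit on the claim: the text does not prove that fall-only series will be scored as events, only that they can be. It does not remove the point. Section 2.3 states a rule that admits either direction, and the word post-operative shows intent without telling an assessor how to score a raised baseline.

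Second, a formal analysis plan is promised before analysis, and all three samples are collected under any rule. Nothing is lost if the matter is settled there. That lowers the severity, but Section 7 does not say that the plan will cover endpoint scoring.

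Third, few patients may be affected. Appendix 1 excludes much serious cardiac disease, including relative contraindications such as left main stenosis, moderate stenotic valve disease and hypertrophic cardiomyopathy. This stands too. The documents give no prevalence of raised baseline, no assay variation and no count of fall-only series.

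A reader might infer that the trial is underpowered, that the AUROC will be biased in a known direction, or that the sample size is wrong. The documents support none of these. The event counts above are assumptions, the bias can run either way, and 90 and 95 both reproduce.

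A reader might also infer that the myocardial infarction definition in Appendix 3, which has the same undirected wording, needs the same change. It does not: it also requires clinical evidence of ischaemia, and it feeds major adverse cardiac events up to 1 year. A day 1 or day 2 rise rule could not classify those later events.

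**Conclusion.** The point holds as a defect in the written rule. Section 2.3 accepts a decrease, includes the baseline sample and does not require the raised value to be post-operative, so a fall-only series can be labelled as post-operative myocardial injury. No visible section prevents this.

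Confidence is high that the wording allows it and low about how many patients it would affect, which may be close to zero. The figures for one or two events (AUROC 0.69 or 0.68; power 77–79% or 73–76%, from 81%) are illustrations. They rest on the assumed count, on no association with heart rate recovery, and on a true AUROC of 0.70. It should be fixed because the primary result depends on about 22 labels and the correction is cheap.

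**What to change.** Amend Sections 2.3 and 3.1, and carry the same wording into the statistical analysis plan before data are analysed:

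1. For the primary endpoint, require at least one day 1 or day 2 troponin that is above the assay's 99th centile and at least 20% above the pre-operative value.
2. Classify a raised troponin with no post-operative rise as chronic elevation, not an event.
3. State how a patient with no pre-operative sample is scored, for example by the day 1 to day 2 change.
4. State how a rise under 20% followed by a fall over 20% is scored, for example as a non-event in the primary analysis and an event in the sensitivity analysis.
5. Report the two-directional rule as a sensitivity analysis, with the number of patients reclassified.
6. Leave the myocardial infarction definition in Appendix 3 unchanged.

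The cost is a few sentences and no new samples. There may be slightly fewer events, and some comparability with the cited two-directional criterion is lost. Whether the 24.5% planning incidence used the same rule cannot be seen. Power does not always return to 81%: if fall-only events had been counted in place of true ones, it is 79.8% or 78.3% after removing one or two. Random rises in chronically raised patients would still be counted (about 1% of them at a CV of 5%, 16% at 10%), so the change removes fall-only labels and not every false label.

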### **3. Objectives and outcomes measures**

#### **3.1 Primary outcome measures**

Post-operative myocardial injury as defined by the 4th Universal definition of Myocardial Infarction, with troponins measured pre-operatively and on days one and two post-operatively.

#### **3.1.1 Rationale for primary outcome**

Post-operative myocardial injury is a well-recognised and widely used outcome measure of the cardiovascular effects of surgery and anaesthesia. It is independently associated with an increased risk of post-operative death in the absence of myocardial infarction. Troponin assays are a relatively cost-effective test to add to the peri-operative blood tests the majority of patients will undergo as part of their routine care. Recent studies have demonstrated that approximately 90% of troponin elevation occurs within the first two days post-operatively.

#### **3.2 Secondary outcome measures**

- Post-operative complications at day 7 based on and including StEP-COMPAC cardiovascular complications, post-operative pulmonary complications, infection, cognitive dysfunction, and acute kidney injury.
- Composite outcomes: major adverse cardiac events (MACE) and major adverse kidney events (MAKE) at days 7 and 30

- Patient-centred outcomes: quality of recovery scale 15 (QoR-15), EQ-5D-5L score, days alive and out of hospital (DAOH) at day 30 and after 1 year
- Clinical indicators: mortality at day 30 and after 1 year, admission to ICU at day 14, readmission to hospital at day 30 and length of hospital stay (with/without in-hospital mortality)
- CPET sub-study: comparison of maximal and submaximal heart rate recovery, plus HRR versus CPET derived indices (AT, VO2peak, and VE/VCO2 at AT). We will also examine patients' perceptions of both tests.

### 3.2.1 Rationale for secondary outcomes

Poor functional capacity has been associated with post-operative morbidity. StEP-COMPAC aims to standardise and clearly define a set group of outcomes to facilitate comparison between studies. Therefore, all secondary outcomes reflect criteria within the current StEP-COMPAC endpoints, with outcomes of relevance to clinicians but also to patients.

## 4. Selection and withdrawal of study participants

### 4.1 Inclusion criteria

1. Provision of informed consent
2. Age >50 years
3. Able to walk unaided
4. Planned elective intermediate/high risk surgery as defined by European Society of Cardiology/European Society of Anaesthesiology (ESC/ESA) guidelines (Table 3)

Table 3 Reproduced from ESC/ESA non-cardiac surgery guidelines

Low-risk: < 1%	Intermediate-risk: 1-5%	High-risk: > 5%

 
• Superficial surgery
 
• Breast
 
• Dental
 
• Endocrine: thyroid
 
• Eye
 
• Reconstructive
 
• Carotid asymptomatic (CEA or CAS)
 
• Gynaecology: minor
 
• Orthopaedic: minor (meniscectomy)
 
• Urological: minor (transurethral resection of the prostate)
 
	
 
• Intraperitoneal: splenectomy, hiatal hernia repair, cholecystectomy
 
• Carotid symptomatic (CEA or CAS)
 
• Peripheral arterial angioplasty
 
• Endovascular aneurysm repair
 
• Head and neck surgery
 
• Neurological or orthopaedic: major (hip and spine surgery)
 
• Urological or gynaecological: major
 
• Renal transplant
 
• Intra-thoracic: non-major
 
	
 
• Aortic and major vascular surgery
 
• Open lower limb revascularization or amputation or thromboemboectomy
 
• Duodeno-pancreatic surgery
 
• Liver resection, bile duct surgery
 
• Oesophagectomy
 
• Repair of perforated bowel
 
• Adrenal resection
 
• Total cystectomy
 
• Pneumonectomy
 
• Pulmonary or liver transplant
 

